#### Aim of this project: we will advise you where to go

The aim of this project is to deliver the most appropriate care for patients presenting at the ED. To achieve this objective a triage nurse will assess all patients presenting at an ED and advise them on the most appropriate point of care: GPC or ED. Triage is 'the sorting out and classification of patients to determine priority of need'. Extended triage is triage combined with allocation to either ED or GPC, which is new in Flanders.

Many EDs in Flanders use the Manchester Triage system (MTS) in their regular care for triage within the ED, to sort patients according to the urgency of their presentation. We developed an extended MTS (eMTS) which foresees allocation to either ED or GPC. Scientific research is crucial to evaluate such triage systems before implementation is possible. Our study is a cluster-randomised trial. During one year, we will perform extended triage using the eMTS at one ED/GPC collaboration. Every month one weekend will serve as a control: the patient does not get an allocation advice.

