#### Design of the clinical trial

#### A controlled longitudinal prospective intervention trial

To answer the above-mentioned research questions we need a longitudinal prospective intervention trial.

To allow definitive conclusions for our questions we need a control group. Historical controls will have too much confounding (not all data is available, the ED was organised in a different way, the GPC was unknown for many patients). Individually randomised controls are impossible from a practical point of view and because of contamination (patients will talk to each other and will not understand why some get a GPC advice and others not). Finally, randomisation by shift is not possible because they overlap in time. Therefore, randomisation is only possible by weekend. We will roll out one control weekend out of every four intervention weekends.

During a control weekend, all data registration and collection will be the same as during intervention weekends but we will not inform patients about their allocation advice. The emergency physician will see all patients deciding to stay at the ED, without influence of the triage advice. As in standard clinical care, patients will have the right to change their mind and go spontaneously to the GPC. Another difference is the communication to the patient: during intervention weekends, we will inform them about the intervention using leaflets and broadcasting in the waiting room of the ED. During control weekends, we will only inform about MTS-triage in general but no about the GPC. We will always mention the iCAREdata opting-out procedure.

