#### **Inclusion and Exclusion**

We will systematically include all patients presenting at the ED during the weekend (the GPC is only open during the weekend starting from Friday 7 pm until Monday 6 am). By presentation at the ED we mean the patient is registered by the receptionist of the ED as a patient. Patients who just pass the ED to enter the hospital or who go directly to a medical department (e.g. obstetrics) are thus not included. The availability of a Belgian citizen national insurance number is the only inclusion criterion. This number is necessary to send the data needed for this study to the iCAREdata database. For the vast majority of patients this number is available. It will not be available for patients who present for the first time at the hospital and forgot all official documents. For patients without a Belgian identity (foreign citizens without Belgian health insurance, people without a legal status and babies less than one week old) the number is never available. The EDs own software allows us to calculate the number of excluded patients.

Patients arriving at the ED by an ambulance with a doctor or nurse (in Dutch called MUG or PIT) is the only exclusion criterion (these patients have already passed through a sort of triage). We estimate an exclusion rate of 15 patients per weekend.

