# Methodology for the medical aspect

The data necessary for this work package are part of a routine clinical report. We will use three types of these reports: triage-consultation reports, ED consultation reports and GPC consultation reports. We will collect these data using the iCAREdata database. This database can link our three types of clinical reports using an irreversibly coded national number. Due to data protection rules, the iCAREdata data manager will execute all queries and only aggregated results will be transferred to the researchers. For more complex statistical analysis, the data manager will transfer an analysis specific table or the analysis will be carried out on the computer of the data manager in cooperation between the researcher and the data-manager. A detailed data management plan is available. The correctness of a triage decision depends on the patient's situation:

- At the GPC (patients compliant to a GPC advice or non-compliant to an ED advice): the ratio of patients referred to an ED to the total number of patients coming from the ED of AZ Monica.
- At the ED (patients compliant to an ED advice or non-compliant to a GPC advice): the physician will answer the same question for all patients: "Should this patient better go to the GPC?". The correctness is defined as the ratio of the patients with a positive answer to this question to the total number of patients staying at the ED after triage.

The parameters of interest in questions 1 through 8 are (conditional) proportions, which calls for analysis by a non-linear model (e.g. binary logistic regression). The study design results in the creation of nested data, where patients are nested in weekends, and weekends are nested in (multiple) nurses. Appropriate analysis of such auto-correlated data requires a nonlinear mixed model. During the first months, data will be used to produce point-estimates of these proportions (e.g., patients seen by GP, correct triage decisions, all false positives, type 1 false positives, patients left without being seen, etc.). With increasing duration of the study, incoming data will be used to explain variability of these probabilities in terms of patient background characteristics, operating nurses/emergency physician, season, etc. Statistical assistance will be called for in order to conduct these analyses.

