# Methodology for the financial aspects

Resources are scarce and therefore it is essential to look at both outcome and resource use when introducing new treatments or treatment paths. This project incorporates both sides. We will use HIS expenditure data (including the share paid by the patient) to get a first insight in the changes in resource use due to the extended triage. Expenditures will be limited to the expenditures of the OOH consultation. In this way, we gain insight in the short-term impact of the new triage system on medical costs from the point of view of the patient and the HIS. For this aspect, we only focus on ambulatory patients (not admitted to the hospital). Although some inpatients can also present at the ED; admitted patients have far more complicated costs and they are not the focus of this project.

In our research we will make use of a cluster randomized trial to get an unbiased estimate of the difference in expenditures due to the extended triage. Randomization allows to measure the impact of the extended triage on average expenditures per patient (research question 9) or specific types of average expenditure per patient (research question 11) by comparing these average expenditures per patient between the intervention weekends and the control weekends. Information on the expenditures of consultations of the GPC are collected in the iCAREdata database. Expenditures generated by the ED are not yet routinely collected for research purposes, but billing data are available and these will be used. We will calculate the averages and use a t-test to test statistical significance. Medical bills also contain detailed information of the nomenclature codes (these are the codes used by the HIS, describing reimbursed care and reimbursement tariffs), performed during an ED visit. We will aggregate these interventions in similar groups such as consultation fees, medical imaging, clinical biology and so on. We will then compare these average expenditures per patient for the various aggregates between the intervention weekends and the control weekends (research question 10) and use a t-test for statistical significance.

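### The plan describes weekends as nested in nurses, but nurse and weekend are crossed and the weekend is randomised; a literal nested fit would understate between-weekend standard errors if weekends vary

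*Combined protocol and SAP*

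**What the plan says.** The section *Methodology for the medical aspect* covers the analysis of questions 1 to 8. It says that "patients are nested in weekends, and weekends are nested in (multiple) nurses" and concludes: "Appropriate analysis of such auto-correlated data requires a nonlinear mixed model". It lists no random-effect terms. The same paragraph proposes to explain variation by, among other things, nurse, emergency physician and season, and it foresees statistical help.

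Other sections describe the design:

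- **Unit of randomisation.** *Design of the clinical trial* rules out shifts ("Finally, randomisation by shift is not possible because they overlap in time") and concludes: "Therefore, randomisation is only possible by weekend". The trial is called cluster-randomised in the overview ("Our study is a cluster-randomised trial") and again under the financial methods ("In our research we will make use of a cluster randomized trial").
- **Length of a weekend.** *Inclusion and Exclusion* gives "the weekend starting from Friday 7 pm until Monday 6 am".
- **Site and duration.** "During one year, we will perform extended triage using the eMTS at one ED/GPC collaboration".
- **Nurses.** Question 1.3 studies the triage nurses on duty as a determinant. *Sample size* expects nurses to improve with practice over the study.

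**The concern.** Strict nesting of weekends in nurses would require each weekend to belong to a single nurse. The design does not allow that.

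The consequence depends on how the clause is turned into a model. A literal reading gives a nurse effect plus a separate effect for each nurse-weekend combination. No term is then shared by all patients of one weekend. Patients triaged by different nurses in the same weekend count as independent, apart from the nurse effects, although the weekend was randomised as a whole. Any real weekend effect is treated as if it averaged out over the nurses on duty.

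This affects only contrasts between weekends: question 1 (width of the interval), season (1.5), question 5 and question 7. Determinants that vary within a weekend and the purely descriptive proportions are outside this point.

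**Working it through.** **Step 1: is the structure nested or crossed?** Friday 7 pm to Monday 6 am is 5 + 24 + 24 + 6 = 59 hours. With overlapping shifts, one nurse cannot cover that, so each weekend has several nurses. With one ED, a full year of weekends and nurses who gain experience, each nurse works several weekends. Nurse and weekend are therefore crossed. This is inferred from the documents, which do not state it.

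**Step 2: is there a figure in the plan to reproduce?** The plan gives no standard error or variance component. Its only related statement is that two weekends suffice for the primary question. It gives no inputs for that, so it cannot be reproduced.

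**Step 3: inputs.**

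- From the documents: 8000 weekend patients a year and 15 exclusions per weekend, so n = 8000/52 − 15 ≈ 139. Fewer than 5 patients per weekend leave without being seen after triage (below 5/139 = 3.6%).
- Assumed: 12 control and 40 intervention weekends; k = 3 to 6 nurses per weekend; weekend SD s = 0.2 or 0.3 (logit); primary proportions 2% v 10%; a 10% share for season and question 7.

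**Step 4: formula.** The sampling variance of a weekend's logit is e = 1/(n p(1−p)). The variance per weekend is s² + e in truth and s²/k + e under the nested fit. Each is divided by the number of weekends in its arm, and the arms are summed. The ratio is √(nested/true). Nurse variance is ignored.

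*Primary, s = 0.3, k = 3.* e = 1/(139 × 0.02 × 0.98) = 0.367 for control and 1/(139 × 0.10 × 0.90) = 0.080 for intervention.

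- True: (0.090 + 0.367)/12 + (0.090 + 0.080)/40 = 0.0423
- Nested: (0.030 + 0.367)/12 + (0.030 + 0.080)/40 = 0.0358
- Ratio: √(0.0358/0.0423) = 0.92

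*10% share, s = 0.3.* With equal proportions the split of weekends cancels. k = 3: √((0.030 + 0.080)/(0.090 + 0.080)) = 0.80. k = 6: √((0.015 + 0.080)/(0.090 + 0.080)) = 0.75.

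| Contrast | SD 0.2 (3 to 6 nurses) | SD 0.3 (3 to 6 nurses) |
|---|---|---|
| Primary, 2% v 10% | 0.96 to 0.95 | 0.92 to 0.90 |
| Left without being seen, 3 per weekend | 0.96 | 0.93 to 0.91 |
| Left without being seen, ceiling of 5 | 0.94 to 0.93 | 0.89 to 0.86 |
| Season, or ED side of question 7, 10% share | 0.88 to 0.85 | 0.80 to 0.75 |

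Splits of 10/42 or 13/39 weekends change the ratios by less than 0.01. At SD 0.3, a 5% share gives 0.87 to 0.83 and a 20% share 0.75 to 0.67.

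**Step 5: the GPC side of question 7.** At 2% v 10%, study patients at the GPC number about 139 × 0.02 ≈ 3 and 139 × 0.10 ≈ 14 per weekend. For a 10% share, e = 1/(3 × 0.09) = 3.70 and 1/(14 × 0.09) = 0.79. At s = 0.3, k = 3: true = (0.09 + 3.70)/12 + (0.09 + 0.79)/40 = 0.338; nested = (0.03 + 3.70)/12 + (0.03 + 0.79)/40 = 0.332; ratio 0.99. Sampling error dominates. The ED keeps about 136 and 125 patients, and its ratio stays at 0.81 to 0.75.

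**Step 6: simulation.** There were 1500 datasets per setting, with an assumed pool of 15 nurses and nurse SD 0.25. Both logistic mixed models were tested at 1.96. Error rates of a nominal 5% test at SD 0.3, nested v crossed:

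| Contrast | 3 nurses | 6 nurses |
|---|---|---|
| Primary (non-coverage) | 8.9 v 6.9% | 8.5 v 5.3% |
| Left without being seen, 3 per weekend | 6.1 v 5.1% | 7.9 v 5.5% |
| 10% share, 12 v 40 weekends | 11.3 v 4.7% | 13.3 v 5.3% |
| Season, 20 v 20 weekends | 10.8 v 5.5% | 15.1 v 5.9% |

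Monte Carlo error is 0.5 to 0.9 points per rate. With zero weekend variance the nested fit shows no loss (4.0 to 5.5%).

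**Step 7: second method.** Generalised least squares on nurse-weekend cells (10% proportion, 5 nurses per weekend, nurse SD 0.3) gave ratios of 0.86 at SD 0.2 and 0.77 at SD 0.3. The ratio was 1.00 when weekends did not vary or when one nurse covered each weekend.

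**The case against.** **No faulty model is specified.** The clause describes data, and the model sentence names no random effects. The word in brackets may point to a multiple-membership model, which keeps the weekend whole. The same paragraph and question 1.3 also treat nurse as an explanatory factor. With nurse as a fixed effect and weekend as a random intercept, the problem does not arise. All of this stands. A reader might infer that the plan prescribes an invalid analysis; the documents do not support that. They show a clause that does not fit the design and that allows both a sound and an anti-conservative implementation.

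**Little is at stake for the main result.** This also stands. A reader might infer that the primary finding is at risk. But with the assumed 2% v 10% shift, weekend-level tests that respect the randomisation were significant in every simulated dataset. Only the interval width is in question. Left without being seen is affected only slightly at realistic rates.

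**The larger effects fall on lesser questions.** A reader might extend the 0.80 to 0.75 ratio to all of question 7, but Step 5 shows that it applies only to the ED side. Season is not randomised and is observed over a single year while nurses gain experience. The correction does not cure that confounding.

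**The size is not anchored in the documents.** Weekend SD, nurse numbers and most proportions are assumed. That limits any claim about magnitude. It does not remove the mismatch between the clause and the design.

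**Conclusion.** The concern holds in conditional form. The stated structure does not match a design in which nurse and weekend are crossed and the weekend is randomised. Two conditions are needed for harm: a literal nurse plus weekend-within-nurse fit, and real variation between weekends. The documents establish neither.

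Under the assumed values the standard error is understated by about 4 to 10% for the primary question, 4 to 9% for left without being seen at 3 per weekend, and 12 to 25% for season and the ED side of question 7. For study patients at the GPC the understatement is about 1% or less. The practical risk is a small or null difference in season or in the ED's reasons for attendance and diagnoses being reported as real. It is not a reversal of the primary conclusion.

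The wording should be corrected before analysis, because this is the plan's only description of the clustering and the analyst will rely on it.

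**What to change.** Replace the clause with: *patients are cross-classified by weekend and triage nurse*. Fit the logistic mixed model with a weekend random intercept, always retained because the weekend is the randomised unit, plus a crossed nurse term. If multiple membership or nurse as a fixed effect was intended, saying so and keeping the weekend as an undivided random effect also resolves the point.

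The cost is one sentence and one line of model syntax. No new data are needed: weekend follows from arrival time, and triage nurse is already a planned variable for question 12. The downside is somewhat wider intervals when weekends vary.

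A small-sample or permutation method for the roughly 12 control weekends is an optional sensitivity analysis and not part of this correction. In the SD 0.3 settings the crossed model tested at 1.96 had error rates of 4.7 to 6.9%. A permutation test would have to follow the actual randomisation scheme, so that scheme would need to be kept on file.

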# Methodology for the financial aspects

Resources are scarce and therefore it is essential to look at both outcome and resource use when introducing new treatments or treatment paths. This project incorporates both sides. We will use HIS expenditure data (including the share paid by the patient) to get a first insight in the changes in resource use due to the extended triage. Expenditures will be limited to the expenditures of the OOH consultation. In this way, we gain insight in the short-term impact of the new triage system on medical costs from the point of view of the patient and the HIS. For this aspect, we only focus on ambulatory patients (not admitted to the hospital). Although some inpatients can also present at the ED; admitted patients have far more complicated costs and they are not the focus of this project.

In our research we will make use of a cluster randomized trial to get an unbiased estimate of the difference in expenditures due to the extended triage. Randomization allows to measure the impact of the extended triage on average expenditures per patient (research question 9) or specific types of average expenditure per patient (research question 11) by comparing these average expenditures per patient between the intervention weekends and the control weekends. Information on the expenditures of consultations of the GPC are collected in the iCAREdata database. Expenditures generated by the ED are not yet routinely collected for research purposes, but billing data are available and these will be used. We will calculate the averages and use a t-test to test statistical significance. Medical bills also contain detailed information of the nomenclature codes (these are the codes used by the HIS, describing reimbursed care and reimbursement tariffs), performed during an ED visit. We will aggregate these interventions in similar groups such as consultation fees, medical imaging, clinical biology and so on. We will then compare these average expenditures per patient for the various aggregates between the intervention weekends and the control weekends (research question 10) and use a t-test for statistical significance.

Currently, the ED's software package sends all nomenclature codes except those for clinical biology and medical imaging to the financial department of the hospital, where the actual bills are made. The financial department draws up the bill, taking into account regulations; e.g. sometimes, regulation prohibits to bill two nomenclature codes simultaneously; the department then decides which one to charge.

To gain more insight in differences in expenditures for different patient groups (research questions 9 and 11), we need demographic and medical diagnostic information of the patient, which is not available on the invoices and is not accessible by the financial department of AZ Monica. We will therefore proceed as follows. We will make a table of all included patients with the following columns: time of arrival at the ED, year of birth, gender, ZIP-code and a new serial number created by us. We will transfer these data using encrypted messages. Because the financial department already has these data to make the invoices this does not raise any new privacy issues. The financial department will search for these included patients and deliver us a datasheet with all the information of the actual invoices linked to this new serial number but without any additional personal data. The nomenclature codes of the interventions performed at the ED can be transferred using iCAREdata.

If the reconstructed bills prove to be valid, research questions 10.1, 10.2. and 12 can be addressed with the variables collected in iCAREdata. For questions 10.1 and 10.2, we will calculate expenditures per patient (for the HIS and the patient) for urgency categories blue and green separately, and for urgency categories red and orange and compare them between the intervention and control weekends, using a t-test to test for statistical difference.

For research question 12 we will perform a multivariate regression analysis, explaining the expenditures (dependent variable) with three sets of explanatory variables: general background characteristics of the patient (age, sex, insurance status), diagnostic information (urgency code, chosen eMTS flowchart) and system characteristics (occupancy rate ED, time of the day, triage nurse, intervention or control weekend). The coefficient for the dummy variable indicating an intervention weekend then gives the impact of the extended triage. It should confirm the effect found in 8. The inclusion of control variables, when estimating the impact in our regression, however reduces residual standard deviation and thus improves the precision

of the estimate. The coefficients on the other variables give a further insight in the additional determinants of expenditures. The regression analyses will be performed on the computer of the data manager using STATA.

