We are mostly interested in false positive 1: patients who complied with the advice GPC but should have stayed at the ED. Some of these patients might be subject to a safety risk. For example, a patient with a heart attack allocated to the GPC might lose valuable time. This category is the same as the proportion of study patients allocated to the GP but referred back to the ED. We will give this category special attention in our process analysis.

Finally, we are also interested in the category correct decision 2: patients who are not compliant to a correct GPC advice. These patients made an inefficient decision so there is room for improvement.

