#### *Research questions:*

- 2. What is the validity of the eMTS as a preliminary diagnostic instrument to detect a primary care patient?
  - 2.1. What is the proportion of correct extended triage decisions measured by comparing the triage advice with the urcenty evaluation of the physician?
  - 2.2. What is the proportion of correct extended triage decisions with advice GP measured by the proportion of referrals within this category?
  - 2.3. What is the proportion of patients wrongly assigned to GPC (all false positives)?
  - 2.4. What is the proportion of patients wrongly assigned to GPC who did go to the GPC (type 1 false positives)
- 3. What is the proportion of patients who are not compliant to a correct GPC advice (Correct decision 2).
  - 3.1. What are the determinants for this non-compliance? (same determinants as studied in question 1.1-1.4)
- 4. What is the proportion of patients in which the nurse gives another advice comparing to the eMTS?
- 5. Does the intervention influence the number of patients left without being seen?
- 6. What is the shift in workload during the different phases of this study for all participating healthcare providers (GPs, triage nurses and ED physicians)?
- 7. Does the epidemiology in terms of reasons for encounter and diagnoses at both OOH services differ between intervention and control weekends?
- 8. What is the proportion of patients who return to the ED within two weeks for each of the categories described in table 2?

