#### Financial aspect

Hypothesis: The extended triage intervention leads to an overall reduction in expenditures for the Health Insurance System (HIS) and the patient. The size of this reduction is determined by the presenting complaint (eMTS flowchart and urgency category), diagnosis, time of the day and patient characteristics.

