#### Recruitment strategy and expected dropout

Unlike most trials, we do not foresee any recruitment problems. In 2016, 8000 patients presented themselves during the weekend at the ED.

For each patient the study period is the time between presentation at the ED and discharge at either the ED or the GPC. This is a time span of only a few hours so the dropout rate will be negligible. Only when a patient leaves the site before consultation at the ED or GPC he or she is a dropout. This number of patients leaving the ED without being seen after triage (i.e. dropouts) is one of the safety indicators we will study. The number of these patients is currently less than five per weekend. We are able to measure this number using the triage reports through iCAREdata. Patients who leave without being seen before the triage-consultation will not be analysed.

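### The cost analysis does not assign the ED bill of patients sent to the GPC and referred back, so the saving could be overstated

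*Combined protocol and SAP*

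**What the plan says.** The hypothesis under Financial aspect reads: "The extended triage intervention leads to an overall reduction in expenditures for the Health Insurance System (HIS) and the patient". It names no time horizon. Methodology for the financial aspects sets the scope: "Expenditures will be limited to the expenditures of the OOH consultation". It covers ambulatory patients only. It describes the result modestly, as a way to "get a first insight in the changes in resource use due to the extended triage" and as a step by which "we gain insight in the short-term impact of the new triage system on medical costs". The same section uses the cluster-randomised design "to get an unbiased estimate of the difference in expenditures due to the extended triage".

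The medical part of the protocol recognises later ED contacts. In the discussion of Table 2, the category of greatest interest (false positive 1) is equated with patients "allocated to the GP but referred back to the ED", and Methodology for the medical aspect measures the referral ratio at the GPC. Research question 8 asks: "What is the proportion of patients who return to the ED within two weeks". The financial methodology attaches no cost to either event.

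Two further passages bear on the referral bill. Under Recruitment strategy and expected dropout: "For each patient the study period is the time between presentation at the ED and discharge at either the ED or the GPC". The invoice request in the financial methodology identifies included patients by ED arrival time, birth year, gender and ZIP code.

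**The concern.** A patient who follows GPC advice and is then referred back generates two bills, one at the GPC and one at the ED. The plan does not say whether the second bill belongs to the index patient, counts as a new included presentation, or falls outside the outcome. Because invoices are found by ED arrival time, a second arrival could be missed or could enter as an extra patient.

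The choice is not neutral between arms. Under Design of the clinical trial, control patients receive no allocation advice and reach the GPC only if they go of their own accord, so the two-bill pathway belongs mainly to intervention weekends. If the second bill is lost, the patient who cost the most along this route is recorded as a saving. Randomisation does not remove that error, because it arises from how the outcome is defined after allocation.

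**Working it through.** **Inputs.** The documents give no cost, expected saving, referral-back rate or return rate, so there is no figure to reproduce. All values below are assumptions, in units of the index ED cost:

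- g: cost of the GPC visit
- k: cost of the later ED contact
- r: excess later ED contacts per diverted patient, compared with similar control patients
- d: share of patients diverted

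**Step 1: one referred-back patient.** Had this patient stayed at the ED, the cost would be 1. Diverted and referred back, the cost is g + k. Take g = 0.4 and k = 1.

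- Both bills counted: saving = 1 − g − k = 1 − 0.4 − 1 = −0.4, a loss.
- ED bill dropped: recorded saving = 1 − g = 0.6.
- ED bill as a separate presentation: the total is right, but the denominator grows by one.

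**Step 2: the intervention-arm average.** Add d = 0.20 and r = 0.05, with no such referrals in control weekends, where the mean is 1.

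- Both bills, one patient: mean = 1 − 0.20 × 0.6 + 0.20 × 0.05 × 1 = 0.89; saving 0.11.
- Bill dropped: mean = 1 − 0.20 × 0.6 = 0.88; saving 0.12. Overstated share = 0.01/0.12 = 8.3%.
- Separate presentation: mean = 0.89/(1 + 0.20 × 0.05) = 0.89/1.01 = 0.8812; saving 0.1188. Overstated share = 0.0088/0.1188 = 7.4%.

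Counting the return as another patient therefore inflates the saving almost as much as losing the bill.

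**Step 3: general form when the bill is dropped.** The recorded saving is d(1 − g) and the full saving is d(1 − g − r·k). The overstated share is r·k/(1 − g); d cancels. At k = 1:

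| r | g = 0.2 | g = 0.4 | g = 0.6 | g = 0.8 |
|---|---|---|---|---|
| −2% | −2.5% | −3.3% | −5% | −10% |
| 0 | 0 | 0 | 0 | 0 |
| 2% | 2.5% | 3.3% | 5% | 10% |
| 5% | 6.25% | 8.3% | 12.5% | 25% |
| 10% | 12.5% | 16.7% | 25% | 50% |
| 20% | 25% | 33.3% | 50% | 100% |

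**Step 4: when the saving disappears.** Break-even is r = (1 − g)/k. At k = 1 this is 80%, 60%, 40% and 20% for g = 0.2, 0.4, 0.6 and 0.8. At k = 2 it is 40%, 30%, 20% and 10%.

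**Step 5: sign of r.** For GPC-to-ED referrals, the control-weekend count is limited to spontaneous movers, so r should be positive. For other returns within two weeks, both arms have them, both are uncosted, and no document indicates which arm has more. There r may be positive, zero or negative.

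**The case against.** The scope is disclosed. The plan states the limit, calls the result short-term and a first insight, and closes each patient's study period at discharge. A longer cost horizon is then a preference unless the plan promises one. A reader might infer such a promise from *overall* in the hypothesis. The documents do not compel that reading: the next sentence says the reduction varies by complaint, diagnosis, time of day and patient characteristics, and questions 9 and 10 move from all ambulatory patients to groups. *Overall* can mean across patient groups and across the two payers. This part of the objection stands.

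It is also fair to say that omission of the referral bill is not established. A weekend ED visit after referral is itself OOH care, and the request asks for full invoice information on included patients. But that leaves the bill unassigned, which is a gap in an analysis described as unbiased.

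Finally, a reader might infer that leaving out later contacts favours the intervention in general. The documents do not support that: outside referrals back, the between-arm difference is unknown. The protocol expects safety problems to be rare because the eMTS is risk averse, so r for referrals may be small, and Step 4 shows that erasing the saving usually needs a high excess rate. These points limit the size of the problem and do not settle how the bill is handled.

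**Conclusion.** The concern holds for patients sent to the GPC and referred back to the ED. Their ED bill has no stated place in the outcome, and two of the three possible treatments overstate the saving in a direction that follows from the design. For other two-week ED returns the direction of any bias cannot be stated.

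The size is unknown. The values in the working rest wholly on assumed g, k and r. They show that a modest referral-back rate could matter to the estimated saving without necessarily changing its sign. The documents disclose the short horizon, so this is an incompletely defined outcome, not a concealed one. The financial hypothesis is not the primary one, and the repair is worth making before cost data are analysed.

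**What to change.** Make three changes.

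1. In Methodology for the financial aspects, define the cost unit as the index OOH episode. For a GPC-to-ED referral, count the GPC and ED bills together, as one patient, under the allocation of the index weekend, and do not count the second ED registration as a new patient.
2. Add a sensitivity analysis, in both arms, that costs the ED returns within two weeks identified for question 8 and attributes them to the index weekend's allocation. Control weekends have the same data registration, so the comparison can be made in both arms.
3. Under Financial aspect, state that the main result concerns expenditure of the index OOH episode.

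The cost is two wording changes and a larger invoice request. The present request lists included, and therefore weekend, presentations. Weekday returns would have to be added under the same serial number, using the iCAREdata linkage and the data manager's time. ED contacts at other hospitals would stay uncounted and should be named as a limitation.
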